In 2004, Papadopoulos et al. evaluated cephalometric changes following simultaneous distalization of first and second maxillary molars by a modification of the Jones Jig as a simple intraoral minimal-compliance fixed appliance. They found that the maxillary first molars were distalized to a mean of 1.4 mm. by a rate of 0.37 mm. per month, and tipped distally by a mean of 6.8°. The maxillary second molars were distalized to a mean of 1.2 mm. and tipped distally by a mean of 8.3°. The maxillary third molars did not move but tipped distally by a mean of 4.0°. They recommended third molars extraction to avoid their impaction, especially if the available space is not adequate. As a result of anchorage loss, the maxillary second premolars were mesialized by a mean of 2.6 mm. and tipped mesially by a mean of 8.1°. The overjet increased by a mean of 0.9 mm., and the overbite decreased by a mean of 1.00 mm. The distance from point A to PtV plane was increased significantly by a mean of 0.7 mm., while the SNA angle did not show any significant changes. The distance from point B to PtV plane and SNB angle were increased significantly ⁽⁴⁾.

In 2013, a systemic review evaluated the molar distalization efficiency associated with the second and third molar eruption stage. It had shown that in 1996, Ghosh and Nanda found that there were no significant differences in maxillary first molar movement and the anchorage loss between the group who had erupted maxillary second molars and the group who did not. This indicates that the eruption of the maxillary second molars had minimal effect on the maxillary first molar distalization ⁽⁵⁾.

However, in 2000, Bussick and McNamara found that distalization was most effective in patients with un-erupted maxillary second molars, for maximum distalization with minimal increase in the lower anterior facial height. While, in 2004, Kinzinger et al. found that the degree of the distal tipping of the maxillary first molars was greater in patients with un-erupted second molars. The degree of the distal tipping of the second molars was greater when the third molar bud was located in the direction of movement. They theorized that during distalizing a molar, a tooth bud acts on the mesial neighboring tooth as a fulcrum. They recommended germectomy of the third molar if a more bodily distalization is needed for first and second molars even when the second molars were not banded ⁽⁵⁾.

Finally, in 2006, Karlsson and Bondmark found that in patients with unerupted second molars, the amount of distalization was significantly greater within a shorter time ⁽⁵⁾.

Open coil springs have been used in orthodontic practice for distalizing maxillary molars. They have the characteristic of the ability to exert a long range of constant, light continuous force which is necessary for optimum tooth movement ⁽⁶⁾.

In 1984, Chaconas et al analyzed and compared open-coil-spring force production from continuous load- deflection curves generated for open coil springs of various wire diameter and lumen sizes, and four wire alloys from three manufacturers. They found that with a constant wire size, an increase in the lumen size produced a decrease in force at a given activation. With a constant lumen size and at a given activation, an increase in wire size produced increase in the force. The arch wire shape and size did not show a significant effect for the coil spring with the smaller lumen size. Larger lumen size springs used with rectangular arch wire showed a greater linear range than springs used with smaller round arch wire. Open coil spring with smaller pitch produced less force at a given activation than springs with larger pitch ⁽⁷⁾.

In 1998, Gianelly used a super elastic NiTi coils to move molar distally. He placed the coil between the first premolars and the first molars on 0.016×0.022 wires applying 100 gm. of force. Nance appliance was used for anchorage. It was fixed to the second primary molars in patients in mixed dentition stage or to the first premolars after they had erupted. Gianelly suggested to start non-extraction treatment by distalization in the mixed dentition stage before eruption of the maxillary second molars as the movement is the fastest and the anchorage loss is the least. Also, the E space in the lower arch is available in the late mixed dentition. If crowding is not present, the amount of distal movement of the maxillary molars can be reduced if the lower molars are moved mesially into the E space ^(8,9).

The molar relationship should be overcorrected by approximately 2 mm. Overcorrection is considered a prepared anchorage to compensate for anchorage loss during retraction of premolars, canines and incisors. Forward movement of the molars to the class I position helps to upright the molars. The overjet increased as a result of anchorage loss. Gianelly recommended the placement of 100gm. class II elastics if the overjet increased by more than 2mm. If the second molars are present and the distalization rate is less than 1mm/month, and / or anchorage loss is excessive, he suggested sequential distalization or changing the treatment plan to extraction protocol. He recommended extraction of the third molars if they have erupted or close to erupt as they impede the distal movement of the first molars ^(8,9).

Recently, temporary anchorage devices have been used during upper molar distal movement. They eliminate the reactive forces from the distal force appliance, these prevent the side effects on the anterior anchoring teeth ⁽³⁾.

In 2004, Gelgör et al. investigated the skeletal, dental, and soft tissue changes after using intraosseous screw-supported distalization appliance. The maxillary first molars were distalized efficiently into an over corrected class I relationship. The force system passed occlusal to the center of resistance of the maxillary first molars, producing backward and upward movements and distal crown tipping. The distal movement of the maxillary molars did

not tend to open the mandible due to the intrusive effect. The status of the maxillary second molar or patient age, has no role on the effectiveness of distalization. There was a slight anchorage loss represented by maxillary incisor proclination and increased overjet. This anchorage loss resulted from mesial tipping of the first premolar, which may be caused by instability of the screw, bone elasticity, flexibility of the TPA, or insufficient connection between the TPA and the screw. Gelgör et al, concluded that 88 % of the space created was from molar distalization and the remaining 12 % resulted from reciprocal anchorage loss ⁽¹⁰⁾.

In 2011, Fudalej et al. evaluated the effectiveness of the distalization of molars with temporary skeletal anchorage device (TSAD) and compared the effectiveness of the TSAD reinforced distalizers with tooth-born noncompliance distalizers. The authors findings indicate that the use of TSAD supported distalizers increased the amount of molar distalization, while the maxillary incisors remained stable. They suggested that in patients with TSAD, greater distal tipping of molars might be the result of excessive pressure exerted on the molars by the distalizers as the whole amount of force will act on the molars and no force will dissipate in the anterior direction. Skeletal anchorage system (SAS) showed the slowest distalization rate as the whole maxillary dentition was distalized simultaneously. They also found that, when implant or mini-plate supported distalization appliances are used; presence or absence of the second molars might play a smaller role. Because of the stability of the implant, no forces will dissipate within anterior direction causing mesial movement or tipping of the maxillary incisors ⁽¹¹⁾.

In 2013, a meta-analysis compared the amounts of distalization and anchorage loss of conventional and skeletal anchorage methods in class II malocclusion correction with intraoral distalizers. The authors concluded that variation in distalization time (1.5 – 14.16 months) might be due to variations in the amount of force applied by each appliance and in the severities of class II malocclusion which required different amounts of distalization. Both conventional and bone-anchored systems were effective for molar distalization but they differed in anchorage loss. Intraoral distalizers with conventional anchorage showed anchorage loss because the Nance button and the anterior teeth can't resist the reaction forces of distalization so they move in the opposite direction. Indirect skeletal anchor devices showed an amount of anchorage loss which is smaller than that with conventional distalizing device. This anchorage loss is the result of many factors such as reaction force, bone elasticity or absence of osseointegration of the mini-implant allowing their movement, flexibility of the wire connecting the premolar-mini-implant. Direct skeletal anchor devices allowed spontaneous distal movement of the premolars without anchorage loss probably due to stretching of the inter-septal fibers ⁽¹²⁾.

In 2014, a retrospective study investigated the dentoalveolar and skeletal effects of two distalizing protocols with different anchorage systems, the MGBM system which is a skeletal anchorage system and the pendulum which is a conventional intraoral anchorage system. The skeletal anchorage of the MGBM system allowed a greater posterior displacement compared to the conventional system. Regarding the molar distal tipping, there was no significant difference between the two systems. When measuring the anchorage loss at the premolar level, there was no significant difference between the two systems. The MGBM system exhibited a

significant less anchorage loss measured at the incisors with significantly less proclination. In the MGBM system, the buccal distalizing force resulted in a greater extrusive action on the first molars. These greater molar extrusion and greater amount of distalization leaded to a greater decrease in the SNB angle. This was a transitory effect as a greater amount of the vertical growth in the condylar area compensated the increase of the vertical dimension of the dentoalveolar region ⁽¹³⁾.

In 2015, a study compared two distalizing systems, the MGBM system as an example of indirect skeletal anchorage system and the Distal Screw as an example of direct skeletal anchorage system. MGBM showed a greater amount of molar distalization, less distalization time and a significant distal crown tipping. Although distalization with crown tipping has less resistance to the movement resulting in less treatment time, this increases the anchorage requirement during the subsequent phase of fixed appliance therapy. Premolars showed a mesial movement and incisors showed a slight proclination. This is because of the low rigidity of the metallic ligature connecting the modified trans-palatal arch and the mini-screws. Distal Screw showed a smaller amount of distalization within a greater time and a more bodily distalization, probably due to the rigidity of the appliance. The premolars were distally pulled with a consistent distal probably due to the trans-septal fibers acting mainly on the dental crowns. This might facilitate the reaction of the premolars and canines during fixed appliance therapy ⁽¹⁴⁾.

Therefore, the idea of this study is to evaluate the effect of using coil spring and mini screw anchorage system during maxillary molars distalization.

Objective

The aim of this study is to evaluate the effect of using coil spring and mini screw anchorage system during maxillary molars distalization.

Study methodology

Study population:

This Randomized Clinical study will be conducted on 20 patients with age ranging from 18 to 25 years, selected from the outpatient clinic of the Orthodontic Department, Faculty of dentistry, Ain Shams University.

The subjects will be selected to fulfill the following inclusion criteria:

1. Skeletal class I, or mild to moderate skeletal class II malocclusion.
2. Full cusp or end to end class II molar relationship.
3. Mild to moderate crowding in the upper dental arch and/or increased overjet.
4. Any other indication requiring maxillary molar distalization unilaterally or bilaterally.
5. Full permanent dentition with exclusion of third molars.
6. Both first and second maxillary molars are in occlusion.
7. Normal or horizontal growth pattern.
8. Non-extraction treatment plan.
9. All subjects are free from any dental anomalies as well as periodontal and systemic diseases that may influence orthodontic treatment.

Exclusion criteria:

1. Previous orthodontic treatment.
2. Severe profile convexity requiring orthognathic surgery.
3. High mandibular angle.
4. Severe molar rotation.
5. Poor oral hygiene.
6. Severe carious lesions.

Study procedure:

An informed consent will be signed by the patients before their enrollment in the current study in which the aim of the study, the methodology and possible complications will be clearly described. This research will be reviewed by research ethics committee, Faculty of dentistry, Ain Shams University.

- Full orthodontic records will be taken for patients who meet the inclusion criteria.
These records are:
 - 1- Extra-oral and intra-oral photographs.
 - 2- Orthodontic study casts.
 - 3- Panoramic radiograph: will be used to detect any dental or bone anomalies, general periodontal condition & bone level, stage of eruption & position of third molars.
 - 4- Lateral cephalometric radiograph: will be used to determine skeletal pattern & mandibular plane angle to verify fitting the inclusion criteria.
- Extra orthodontic records: Cone Beam Computed Tomography.
- The randomization will be through computer generated selection software.

Procedure:

- The maxillary first and second molars will be banded. Brackets will be bonded to the maxillary first and second premolars.
- Leveling of these segments will be carried out using orthodontic wires sequentially, till 0.019" x 0.025" stainless steel archwire is reached.
- Segmented stiff 0.019" x 0.025" stainless steel archwire will be used to minimize the distal tipping and rotation of the molars. It will be extended from the maxillary second molar to the maxillary first premolar.
- In the first approach, a nickel titanium open coil spring will be inserted mesial to the maxillary first molar to provide distalizing force. In the second approach, two pieces of nickel titanium open coil springs will be inserted mesial to the maxillary first molar and mesial to the maxillary second molar.
- Mini screw anchorage system will be used as a mean of indirect anchorage.
- The patients will be seen every four weeks for reactivation until Class I molar relationship is obtained, as assessed clinically.

Methods of assessment:

- The rate of tooth movement will be analyzed using computer software on digital models obtained every four weeks. When a Class I molar relationship is obtained distalization will be considered achieved, which will be assessed clinically.
- Cone beam computed tomography (CBCT) will be taken for every patient pre-treatment and post-distalization.

Adverse event reporting

Anticipated adverse effects regarding the use of mini screw and its remedy

1. **Pain and discomfort:** If present, it may last 1–2 days and could be reduced by instructing the patient to use warm mouth rinse containing local anesthetic agent.
2. **Irritation to the buccal mucosa:** Bonding resin or a periodontal wound dressing could be applied to the head of the mini screw to smooth its surface and to minimize soft-tissue irritation.
3. **Inflammation around mini screw:** The screws need to be thoroughly cleaned. Mild infections can be controlled by using antiseptic mouthwash and by regular brushing.
4. **Mini screw mobility or failure:** The patient will be instructed to avoid manipulating the screw with fingers, tongue, or with foreign objects like pens. The mini screw could be tightened and left for 1–2 months with no loading, or light loading if necessary. If stability cannot be regained, the mini screw will be removed and replaced.

Statistical analysis

All gathered data will be tabulated and statistically analyzed.

References

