Document Date: June 23, 2022

Three Dimensional Assessment of Maxillary Molars Following Distalization Using Two Different Approaches

A Thesis
Submitted to Faculty of Dentistry
Ain-Shams University
In Partial Fulfillment of the Requirements of
Master's Degree in Orthodontics

Faculty of Dentistry
Ain Shams University
2022

Statistical analysis

Statistical analysis was performed with SPSS 20^{®*}, Graph Pad Prism^{®**}, and Microsoft Excel 2016^{***}.

All quantitative data were explored for normality by using Shapiro Wilk Normality test and presented as means and standard deviation (SD) values. All qualitative data were presented as frequency & percentage. All data were presented in (43) tables & (38) graphs.

Tests used:

- Comparisons 2 different groups was performed by using Mann Whitney test.
- Comparisons 2 successive follow ups periods was performed by using Paired t-test.
- Comparison between quantitative continuous data (Age & Duration) was performed by Independent t-test.
- Comparison between qualitative dichotomous data (Gender) was performed by Chi square test.
- Reliability test was performed by using Intra-class Correlation Coefficient (ICC).

* Statistical Package for Social Science, IBM, Armonk, NY, USA.

** Graph Pad Technologies, San Diego, CA, USA

*** Microsoft Co-operation, Redmond, WA, USA.

* All results presented as:

I. Normality test.

II. Baseline characteristics:

- A. Age.
- B. Gender.
- C. Duration
- D. Pretreatment measurements. (Appendix IV).

III. Measurements

The following measurements were carried for both group I and group II as well as in comparison between the two groups.

A. Skeletal measurements

- 1. Skeletal antero-posterior measurements.
- 2. Skeletal vertical measurements.

B. Dental measurements

- 1. Angular
- 2. Linear

C. Soft tissue measurements.

IV. Reliability: (Appendix V)

- A. Inter-observer.
- B. Intra-observer.

I. Normality test:

Exploration of the given data was performed using Shapiro-Wilk test and Kolmogorov-Smirnov test for normality. As Listed in (Table 11) and showed in (Figure 53), it was revealed that the significant level (P-value) was shown to be insignificant as P-value > 0.05 , which indicated that alternative hypothesis was rejected, and the concluded data originated from normal distribution (parametric data) resembling normal Bell curve in pre & post measurements while P value was significant in the difference between both groups which indicated nonparametric data.

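### Treatment runs to Class I and entry mixes two starting severities, yet starting molar relationship is neither adjusted for nor shown by arm: a valid comparison that may lose a little precision

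*Protocol*

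**What the plan says.** - **Entry.** The protocol's inclusion criteria accept a "Full cusp or end to end class II molar relationship". A further criterion accepts "Any other indication requiring maxillary molar distalization unilaterally or bilaterally".
- **End of treatment.** Under Procedure: "The patients will be seen every four weeks for reactivation until Class I molar relationship is obtained, as assessed clinically". The end point is an occlusal target, not a fixed time.
- **Background.** The protocol cites a meta-analysis that offers, as one possible reason for variation in distalization time, differences "in the severities of class II malocclusion which required different amounts of distalization".
- **Allocation.** "The randomization will be through computer generated selection software". No stratification is mentioned.
- **Records.** The pre-treatment records include "Orthodontic study casts".
- **Analysis.** The SAP, under Tests used, states: "Comparisons 2 different groups was performed by using Mann Whitney test". Its tables apply that test to pre-post differences. Age and duration get an independent t-test and gender a chi-square test.
- **Baseline.** The SAP lists age, gender, duration and pretreatment measurements; the last are in an appendix that is not reproduced. Starting molar relationship appears in none of the tables shown.

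**The concern.** If every patient is moved to the same end point, one who starts a full cusp away has further to go than one who starts end to end. Part of the spread in molar distance and in duration would then reflect where patients began rather than which spring arrangement they received.

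In arms of 12 and 9 with no stated stratification, the share of full-cusp patients can differ appreciably by chance. An unadjusted comparison carries that difference into the result, where it could imitate or mask a treatment effect. With no table of starting molar relationship by arm, a reader cannot judge whether this happened.

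**Working it through.** **1. Group sizes.** SAP Table 13 gives 2 + 10 = 12 and 3 + 6 = 9 (21 in all, against 20 planned in the protocol). As a check, an independent t-test on duration from Table 14 (8.03, SD 2.90, n = 12; 10.59, SD 3.89, n = 9) gives t = -1.73, P = 0.0995; the SAP states 0.09. The age comparison gives P = 0.095 against a stated 0.09. The sizes fit the SAP's own figures.

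**2. Unadjusted comparison of first-molar distance.** Table 32, MBc6/S Ver: -3.78 (SD 1.31) v -4.51 (SD 3.39), a difference of 0.73 mm.
- Pooled variance = (11 × 1.31² + 8 × 3.39²)/19 = (18.88 + 91.94)/19 = 5.832, so SD = 2.415 mm.
- SE = 2.415 × √(1/12 + 1/9) = 1.065 mm; 95% CI half-width 2.23 mm.
- t-test P = 0.50; the SAP's Mann-Whitney P is 0.8.

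**3. Chance imbalance in severity.** The documents give neither the full-cusp share nor the extra movement needed. Assume a 50% share and a gap g of 1 to 2 mm. With X ~ Bin(12, 0.5) and Y ~ Bin(9, 0.5), the severity-driven difference is g × |X/12 - Y/9|. It reaches 0.73 mm when the shares differ by at least 0.73/g. Exact enumeration:

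| Gap g | Share difference needed | Either direction | Observed direction only |
|---|---|---|---|
| 1 mm | 0.730 | 0.04% | 0.02% |
| 1.5 mm | 0.487 | 2.6% | 1.3% |
| 2 mm | 0.365 | 8.6% | 4.3% |

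At a 30% or 70% share, the either-direction figures are 1.5% (1.5 mm) and 6.7% (2 mm).

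**4. Gain from adjustment.** At a 50% share the severity variance is g²/4, so R² = (g²/4)/5.832. The adjusted SE is multiplied by √(1 - R²) and raised by the factor √(1 + d²/[S(1/12 + 1/9)]). Here d = X/12 - Y/9, and S is the within-arm sum of squares of the severity indicator. The second factor is averaged over the binomial distribution.

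| Gap g | R² | SE cut ignoring covariate cost | Net SE cut |
|---|---|---|---|
| 1 mm | 0.04 | 2.2% | none (-0.6%) |
| 1.5 mm | 0.10 | 4.9% | 2.2% |
| 2 mm | 0.17 | 9.0% | 6.4% |

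At 2 mm the SE falls from 1.065 to about 1.00 mm.

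**5. Why the range stops at 2 mm.** At an even split, a 3 mm gap implies a severity SD of 1.5 mm, above Group I's total SD of 1.31 mm. With 6 of 12 full cusp, the largest gap that fits solves (g/2) × √(12/11) = 1.31, giving g = 2.51 mm with no other variation left. At 2 mm, severity (variance 1.00) is already 58% of Group I's variance (1.716) but only 9% of Group II's (11.492). Severity at these gaps cannot explain Group II's wide spread.

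**6. No tabled variable stands in for severity.** The correlation of baseline MBc6/S Ver with its change is (SD_post² - SD_pre² - SD_diff²)/(2 × SD_pre × SD_diff).
- Group I (Table 30): (3.35² - 3.53² - 1.31²)/(2 × 3.53 × 1.31) = -0.32.
- Group II (Table 31): (5.61² - 3.53² - 3.39²)/(2 × 3.53 × 3.39) = +0.31.

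Pooled within arms, it explains about 1% of the change. This measure places the molar against a cranial reference, whereas Class II discrepancy also depends on the lower molar.

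**The case against.** The strongest reply is that nothing is invalid. Under randomization the unadjusted tests hold their error rate, and covariate adjustment is a refinement. That stands. So does the point that the gain is small and may be nil: in 21 patients, estimating one more coefficient uses up most of what a weak covariate returns.

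A reader might infer that distance is set largely by severity, or that severity is the strongest predictor of outcome. The documents do not show this. The background says only that severity, along with applied force, might explain variation in treatment time, and no correlation with distance is reported.

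A reader might also extend the point to tipping and rotation. The background relates tipping to the line of force, pressure on the molars and appliance rigidity, not to starting molar relationship, so that extension has little support.

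Nor do the documents suggest that the 0.73 mm difference is a severity artefact. The SAP claims no effect there (P = 0.8). Baseline overjet (6.30 v 4.46 mm) and ANB (5.50 v 4.36) differ between arms, so balance cannot be presumed, but neither is the molar relationship and neither difference demonstrates imbalance in it.

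Finally, the covariate is not quite ready to use. Casts exist, but no passage says molar discrepancy is measured in mm, and unilateral and bilateral cases need a rule for forming one value per patient. That is a modest task, not a reason to leave the variable out.

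**Conclusion.** The point holds as a low-cost improvement. Treatment to a common end point, two admitted starting severities and a comparison with no severity term are all in the documents. That distance and duration depend partly on severity is a reasonable inference from the stopping rule and the protocol's background, not a documented result.

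Under the assumed 50% full-cusp share and 1 to 2 mm gap, a severity-driven difference as large as the one observed arises in about 0% to 9% of trials, counting both directions, and adjustment cuts the SE by about 0% to 6%. At an even split a 3 mm gap does not fit Group I's SD; a very uneven split would admit a larger gap. The size calculation pools two very different SDs and uses normal theory in place of Mann-Whitney, so it is indicative only.

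The firmest part is the missing table: without starting molar relationship by arm, a reader cannot tell whether the arms began equally far from the target. The appendix of pretreatment measurements is not available here and might contain it.

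**What to change.** 1. Read starting molar relationship from the baseline casts, as full cusp v end to end or as discrepancy in mm. State a rule for bilateral cases, such as the mean of the treated sides, and say how patients entered under the any-other-indication criterion are coded.
2. Tabulate it by arm with the other baseline characteristics.
3. Add it as the single covariate in a comparison of anteroposterior molar distance and of duration. Use rank-based ANCOVA, or a linear model with heteroscedasticity-robust standard errors given SDs of 1.31 v 3.39.
4. Report the adjusted difference with its 95% CI beside the existing Mann-Whitney and t-test results. Label it post hoc, because the SAP already contains results.
5. Before re-analysing duration, check Table 14. For 12 values between 5.50 and 9.73 the largest possible SD is (4.23/2) × √(12/11) = 2.21, but 2.90 is printed for Group I.

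The cost is one degree of freedom and a small amount of cast measurement, with no new patients, visits or imaging. If severity predicts only weakly there may be no gain in precision, but the baseline table is useful either way.

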Table (11): Normality exploration of both groups regarding all measurements:

Measurements		Group I Single Coil Spring	Group II Double Coil Spring
Skeletal.	Pre	> 0.05	> 0.05
	Post	> 0.05	> 0.05
	Difference	$< 0.05^*$	$< 0.05^*$
Dental	Pre	> 0.05	> 0.05
	Post	> 0.05	> 0.05
	Difference	$< 0.05^*$	$< 0.05^*$
Soft tissue	Pre	> 0.05	> 0.05
	Post	> 0.05	> 0.05
	Difference	$< 0.05^*$	$< 0.05^*$

* Significant difference as $P < 0.05$

[figure not shown]
[figure not shown]

Figure (53): Scattered chart represents normal bell curve of normality test.

II. Baseline characterized:

1. Age:

In group I, minimum age was (18.4), maximum was (21.2), while mean \pm standard deviation was (19.42 ± 1.03) . In group II, minimum age was (18.08), maximum was (23.17), while mean \pm standard deviation was (20.7 ± 2.24) , as presented in table (12) and figure (54).

Comparison between both groups was performed by using Independent t-test which revealed insignificant difference between them as $P > 0.05$, as presented in table (12).

Table (12): Minimum, maximum, mean & standard deviation of age in both groups:

	Min	Max	M	SD	P value
G I	18.4	21.2	19.42	1.03	0.09
G II	18.08	23.17	20.7	2.24	

N: count

Min: minimum

Max: maximum

M: mean

SD: standard deviation

[figure not shown]

Figure (54): Bar chart showing mean of age in both groups.

2. Gender:

In gender all companions were performed by using Chi square test. In group I, male (16.67%) was significantly lower than female (83.3%) as $P < 0.05$, while in group II male (33.3%) was insignificantly lower than female (66.6%) as $P > 0.05$, as presented in table (13) and figure (55).

Also, comparison between group I & II reveled insignificant difference between them in both male & female as $P > 0.05$ as presented in table (13).

Table (13): Frequency & percentage of gender distribution in both groups:

Group	Male		Female		P value
	N	%	N	%	
Group I	2	16.67%	10	83.33%	0.001*
Group II	3	33.33%	6	66.67%	0.13
P value	0.34		0.34		

N: count

%: percentage

P: probability level which is significant at $P \leq 0.05$

[figure not shown]

Figure (55): Bar chart showing percentage of gender distribution in both groups

3. Duration:

In group I, minimum duration was (5.5 months), maximum was (9.73 months), while mean \pm standard deviation was (8.03 ± 2.9) . In group II, minimum duration was (4 months), maximum was (14.9 months), while mean \pm standard deviation was (10.59 ± 3.89) .

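### The protocol's rate-of-movement analysis is missing from the SAP as supplied; Duration is filed as baseline with an impossible Group I row; and 48 unranked between-group tests rest partly on faulty change SDs

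*Protocol*

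**What the plan says.** **Protocol, Methods of assessment.** Two assessments are planned. One is CBCT before treatment and after distalization. The other is rate: "The rate of tooth movement will be analyzed using computer software on digital models obtained every four weeks". The Procedure section sets a variable end point: "The patients will be seen every four weeks for reactivation until Class I molar relationship is obtained, as assessed clinically". Starting severity varies by design, since the inclusion criteria admit "Full cusp or end to end class II molar relationship" and also "Any other indication requiring maxillary molar distalization unilaterally or bilaterally". The protocol names no primary outcome.

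**SAP, outline of results.** It lists normality, baseline characteristics, skeletal, dental and soft-tissue measurements, and reliability. Every measurement table is pre, post and difference. On the measurements it says "The following measurements were carried for both group I and group II as well as in comparison between the two groups". On extent it says "All data were presented in (43) tables & (38) graphs"; the supplied text holds Tables 11 to 41.

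**SAP, Duration.** It is item C under baseline characteristics and is tested together with age: "Comparison between quantitative continuous data (Age & Duration) was performed by Independent t-test". The text reads "In group I, minimum duration was (5.5 months), maximum was (9.73 months), while mean" and then gives 8.03 ± 2.9. Table 14 repeats these values, with 4.00, 14.90, 10.59 and 3.89 for Group II and P = 0.09.

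**The concern.** Treatment continues until a clinical Class I relationship is reached, and both full-cusp and end-to-end cases enter. Total first-molar movement therefore depends heavily on where the patient started and does not show speed. Rate is the planned measure that would, and the supplied SAP does not carry it. What remains is Duration, whose start and end are not stated in the supplied text, which sits among baseline items although it follows randomisation, and whose Group I row cannot be right. The comparison of treatment time (8.03 against 10.59 months) is therefore unverified.

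The between-group results have a separate weakness. Nine tables test changes one by one at 0.05, five results are starred, and the supplied text gives neither a ranking nor a multiplicity rule. A reader would naturally lead with the smallest P, which is the least trustworthy of the five.

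**Working it through.** **Inputs.** Arm sizes 12 and 9 are the male and female counts in SAP Table 13. They reproduce printed paired P values: SNB in Group I gives 0.196 (printed 0.194), and MBc6 in Group II gives 0.0040 (printed 0.004). MBc6 in Group I does not fit: it gives about 0.0000007 against 0.002. However, the P column of Table 30 opens with 78.77, the pre mean of that row, so it may be displaced.

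**1. Ceiling on the Group I Duration SD.** For given min, max and mean, SD ≤ √[(max − mean)(mean − min) · n/(n − 1)].
- √[(9.73 − 8.03)(8.03 − 5.50) · 12/11] = √(1.70 × 2.53 × 1.0909) = √4.692 = 2.17, against 2.90 printed.
- Arm size does not explain it: the ceiling is 2.54 at n = 3 and falls as n rises.
- A wrong mean alone does not explain it: at the mid-range mean the ceiling is (4.23/2)·√(12/11) = 2.21.
- Keeping min, mean and SD, the max must be at least 8.03 + 2.90² × (11/12)/2.53 = 11.08.
- Group II is possible: √(4.31 × 6.59 × 9/8) = 5.65, against 3.89.

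**2. Reproducing the printed P of 0.09.**
- Pooled t-test with SD 2.90: pooled SD = √[(11 × 2.90² + 8 × 3.89²)/19] = 3.353; t = 2.56/[3.353 × √(1/12 + 1/9)] = 1.73; P = 0.0995. This is 0.09 only if truncated. Welch gives 0.119.
- Age, under the same stated test: pooled P = 0.095 (printed 0.09), Welch 0.141. So the test appears to be pooled.
- If instead the SD is the faulty entry, attainable values run from 0.92 (one patient at 5.50, one at 9.73, ten at 8.113) to 2.11 (four at 5.50, seven at 9.73, one at 6.25). Pooled P is then 0.039 to 0.067, crossing 0.05 near SD 1.5. None of these is 0.09, so the printed P would also be wrong.

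**3. The smallest between-group P (U1-tip/S Ver, Table 32: 0.002).**
- The Group II change SD is printed as 0.13. Table 31 gives pre and post SDs of 2.86 and 2.99, and 2.99 − 2.86 = 0.13. The SD of a paired change is not the difference of two SDs.
- The other Group II U1 rows show the same pattern to within 0.01: U1-NA 5.79 − 4.94 = 0.85 (printed 0.85), U1-FHP 4.83 − 4.00 = 0.83 (0.83), U1-apex 3.18 − 3.09 = 0.09 (0.08), U1-tip/PP 3.19 − 3.27 = −0.08 (−0.09, a negative SD).
- With SD 0.13, the paired t is 0.59 × √9/0.13 = 13.6 and P is below 0.000001. Table 31 prints 0.12.
- A pooled t-test on the printed means and SDs gives 0.0023. The same test gives 0.282, 0.616, 0.705 and 0.334 for U1-apex, U1-tip/PP, U1-NA and U1-FHP, against 0.28, 0.61, 0.70 and 0.33 printed. Mann-Whitney is the stated test.
- A paired P of 0.12 on 8 degrees of freedom means t = 1.74, so the SD would be 0.59 × 3/1.74 = 1.02. The pooled between-group P would then be about 0.10.

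**4. Multiplicity, taking printed P values at face value.**
- Count over Tables 17, 20, 23, 26, 29, 32, 35, 38 and 41: 5 + 3 + 6 + 4 + 4 + 12 + 7 + 4 + 3 = 48.
- Starred: 0.002, 0.009, 0.03, 0.04, 0.04.
- Holm: 48 × 0.002 = 0.096; 47 × 0.009 = 0.423; the rest are 1.
- Benjamini-Hochberg: 0.096; 48 × 0.009/2 = 0.216; then 48 × 0.04/5 = 0.384 for the other three.

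**The case against.** **The SAP is an extract.** It declares 43 tables and the text shows 31 (Tables 11 to 41). Rate, a definition of Duration, a lead outcome or a multiplicity rule could sit in parts not supplied. This stands, and each of those statements is limited to the supplied text. A reader might infer that a primary outcome was switched or that rate was suppressed. The documents do not support that: neither names a primary outcome, and the rate results may be elsewhere.

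**Duration is not hidden, and its end can be guessed.** It has its own heading, table and figure, and the protocol says when distalization counts as achieved. This partly stands: the filing is a labelling matter. But the SAP does not tie Duration to that event, and it gives no starting point (records, levelling or spring placement).

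**The impossible row may be a slip in the range.** The printed P fits SD 2.90 with a pooled test, so the calculation may be sound and only the min or max misprinted. This stands as the likelier explanation. A reader might take the 0.039 end of the range to mean that Group I was significantly faster. That needs the SD to be the wrong entry and the printed P to be wrong too.

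**Treating 48 rows as one family is a choice.** It is. With each table as its own family, Holm gives 4 × 0.009 = 0.036 for U5-MSP and 12 × 0.002 = 0.024 for U1-tip/S Ver. The second inherits the SD problem, so only U5-MSP is a credible survivor, and only under that narrower family. Nor does failing adjustment show that the starred differences are absent.

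**Conclusion.** The point holds as follows.

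- A planned rate analysis is unaccounted for in the SAP as supplied.
- Duration is a post-randomisation result filed under baseline, without start or end points there.
- The Group I Duration row is impossible: SD 2.90 against a ceiling of 2.17. This does not depend on the arm size being exactly 12. At least one entry is wrong; the min, max or mean is likelier than the SD, and a wrong mean alone cannot account for it. The non-significant verdict is unverified, not refuted.
- The 48 between-group tests have no stated priority. None of the five starred results survives adjustment across all 48, even with 0.002 at face value, and that P value is itself unreliable. That it came from a t-test on a mis-derived SD is an inference from five matching rows; patient-level data are needed to confirm it.

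The P values recomputed here assume arms of 12 and 9 and the printed means.

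**What to change.** 1. **Rate.** Report the per-patient first-molar rate by arm from the four-weekly models, measured from spring placement, with sides averaged where both were treated, and give the between-arm difference with a 95% CI. Alternatively, cite where it is reported, or state that the models were not taken. Do not substitute CBCT change divided by the time between CBCTs: the first CBCT precedes levelling, so the denominator would include levelling time.
2. **Duration.** State its start and end points, move it to outcomes, check the Group I min, max, mean, SD and the P value against source data, and report the difference with a 95% CI.
3. **Between-group tests.** Recompute the U1 change SDs and P values from patient-level data with the stated test. Then label the 48 comparisons exploratory, state the family, and print adjusted P values beside the raw ones.

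**Cost.** Steps 2 and 3 need a source check and re-tabulation. Step 1 is cheap if rate is already reported. If the models exist but are unmeasured, the printed durations imply 12 × 5.50 to 12 × 9.73, plus 9 × 10.59, or about 161 to 212 patient-months. At one model per 28 days (× 30.44/28) that is roughly 175 to 230 models, a rough figure because one of the duration entries is faulty. The downside is that the starred results become exploratory.
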